4.2 Retrospective track

As described in Section 1.4, Sciensano holds a collection of >5,000 NIPD strains (1995-2015) for which extracted gDNA, complete MIC profile and associated metadata are already available. From every uneven year, we will randomly select 150 isolates, without bias towards age and gender. On these strains, we will perform FT-IR capsular typing, which will have been developed during the first months of this project (section 5.4). Typing of the isolates of the retrospective study will be performed in the summer period of 2021, when few isolates of the ongoing prospective study (2020-2022) are expected.

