1.2 Changing vaccination recommendations in Belgium

In Belgium, the 23-valent polysaccharide vaccine or PPV23 (currently Pneumovax 23®, MSD) is licensed since 1995. It is currently recommended by the Superior Health Council (CSS/HGR) for the prevention of pneumococcal infections in persons ≥ 2 years of age, presenting with an increased risk of mortality and severe morbidity due to pneumococcal infections, and often sequentially combined with PCV13 (Prevenar®, Pfizer) [4]. The national infant vaccination program was initiated in 2007 with PCV7 (Prevenar®, Pfizer), and was updated to PCV13 in 2011. In 2015-2016, the program changed from PCV13 to PCV10 (Synflorix®, GSK). Very recently (HGR 9519, December 2018), a new advice was published by the Superior Health Council which recommended again the use of the 13-valent vaccine in children ≤ 2 years of age, alongside an explicit statement stating that this advice could be reconsidered upon the release of new data.

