1.4 Sciensano holds historical collection of non-invasive pneumococcal isolates

Between 1995 and 2015, [name] (MD, PhD) led a team at Sciensano investigating the evolution of antibiotic resistance in NIPD isolates from CAP patients (as well as from children with acute otitis media). For 12 consecutive winter periods, his team collected between 300 and 500 clinical isolates using a network of 15 peripheral hospital-based laboratories distributed across the country. Consequently, we hold a collection of >5,000 strains for which extracted gDNA, complete phenotypic MIC profiles and associated metadata are already available (**Figure 4** for age distribution). This study, funded by Bayer, focused on antimicrobial resistance and did not routinely include serotyping.

This constitutes an extremely valuable collection that dates from before the introduction of pneumococcal vaccination programs. In the context of the proposed study, this collection would serve to retrospectively assess the impact of successive vaccination campaigns on serotype distribution among NIPD isolates in Belgium.

[figure not shown]

Figure 4. Age distribution of the patients for which cultures were included during the NIPD surveillance study in 2012-2013 using the same network of laboratories [24].

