1.5 Implications for empiric treatment guidelines?

Penicillin and macrolides have been the mainstay in the treatment of respiratory diseases for decades [25], but the worldwide spread of drug-resistant clones translated into increased usage of fluoroquinolones [26,27]. Recently, the World Health Organisation (WHO) included penicillin-resistant *S. pneumoniae* in the list of 12 critical drug-resistant pathogens [28]. Nevertheless, current empiric treatment guidelines support the continued use of penicillin and amoxicillin for drug-susceptible isolates. For risk patients, Belgian Antibiotic Policy Coordination Committee (BAPCOC) recommends use of either a respiratory fluoroquinolone, or combination therapy with beta-lactam antibiotic (high-dose amoxicillin, amoxicillin-clavulanate, or, alternatively, a second- or third-generation cephalosporin) plus a macrolide [29].

Reminiscent of the studies on serotype replacement and global surveillance, studies on pneumococcal drug-resistance are strongly biased towards IPD isolates. However, it is conceivable that the non-invasive population functions as a ‘laboratory’ for the development of drug resistance. During a nation-wide multicentre survey spanning nearly two decades (1995-2014), researchers from Sciensano unequivocally reported higher rates of antibiotic resistance in the non-invasive population, as compared to the invasive strains (**Figure 5**) [30]. Therefore, including antimicrobial resistance screening for non-invasive strains would improve pneumococcal surveillance, improve empiric treatment guidelines and add the possibility to detect circulating drug-resistant clones.

[figure not shown]

Figure 5. Drug non-susceptibility in invasive versus non-invasive *S. pneumoniae* isolates in Belgium (2004-2013). Data from IPD is annually reported by the National Reference Centre for pneumococcal disease. Data for NIPD was collected in the framework of the multicentre study (1995-2014) on drug susceptibility of non-invasive *S. pneumoniae*.

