1.6 Key points

From the information above, it is clear that:

- Current recommendations for vaccination and empiric treatment are strongly influenced by the current surveillance focus on IPD. Information on serotype distribution and drug resistance dynamics in NIPD is scarce. However, a discrepancy in serotype distribution between IPD and NIPD isolates is present in neighbouring countries.
- In Belgium, there was a recent (2015-2016) switch in the infant vaccination program to PCV10 and a recommended reversal to PCV13 in December 2018. The influence on serotype distributions in NIPD is unclear, although this information is essential in vaccine cost-effectiveness analyses [31].

2 Study aims

The main objective of this study is to generate insight in the serotype dynamics for NIPD in Belgium, in association with changing vaccination programs. We aim to serotype non-invasive *S. pneumoniae* isolates prospectively collected in Belgian routine laboratories, during a period of 20 months. Simultaneously, a similar characterisation study will be performed retrospectively on a selection of more than 5,000 NIPD strains collected between 1995 and 2014 in Belgium.

Additionally, this projects aims to do the surveillance of emerging serotypes, clones and drug resistances. Using Whole Genome Sequencing (WGS), the genetic divergences between IPD and NIPD isolates will also be studied, in collaboration with the National Reference Centre (NRC) for pneumococcal diseases (UZ Leuven, Belgium).

3 Type of study

This will be an observational study collecting data on *S. pneumoniae* serotypes causing NIPD in Belgium, in relation with changing vaccination programs.

4 Conducting the study

The study will be conducted by Sciensano in collaboration with the NRC for pneumococcal diseases and 12 peripheral clinical laboratories, which all agreed in writing to prospectively collect non-invasive *S. pneumoniae* samples in the framework of this study. These labs are geographically spread over Belgium to avoid clonal bias in sampling (**Table 1**).

Table 1. Peripheral network of participating clinical laboratories.

Hospital	Contact	City	
CHR Citadelle	Dr. [name]	Liège	
CHU Mont-Godinne	Dr. [name]	Yvoir	
ZNA	Dr. [name]	Antwerpen	
Virga-Jessaziekenhuis	Dr. [name]	Hasselt	
Hôpital de Jolimont	Dr. [name]	Haine-St.-Paul	
AZ Delta	Dr. [name]	Roeselare	
AZ St. Jan	Dr. [name]	Brugge	
AZ. Jan Palfijn	Dr. [name]	Gent	
Imeldaziekenhuis	Dr. [name]	Bonheiden	

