4.3 Gantt Chart

* Intermediate reports will not be published publicly, and can only be consulted by participating hospitals and funding partners.

M1. Ethical Approval granted

M2. FT-IR based capsular typing test validated for 24 pneumococcal serotypes

M3. Protocol approved by all partners

M4. Preparatory phase finished, with Sensititre™ plates received, database and lab shipments completely prepared

M5. Capsular typing completed for selected non-invasive *S. pneumoniae* isolates (1995-2014)

M6. Capsular typing and MIC testing completed for all NIPD isolates collected during 20 months (2021-2022)

M7. Final statistical analyses on complete dataset finished

Publication 1 (provisional title): An FT-IR based test for fast *cps* typing in *Streptococcus pneumoniae*.

Publication 2 (provisional title): The genetic diversity of Belgian invasive and non-invasive *Streptococcus pneumoniae* strains in an international context.

Publication 3 (provisional title): Distribution of serotypes and drug resistance profiles of Belgian non-invasive *Streptococcus pneumoniae* strains in light of national vaccination campaigns

5 Microbiology

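### 150 isolates per uneven year over 1995-2015 is 1,650, not the stated 1,500, and a trend test alone can miss a fall and return of vaccine types across programmes

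*Protocol*

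**What the plan says.** The selection rule is in section 4.2: "From every uneven year, we will randomly select 150 isolates, without bias towards age and gender". The same section gives the span as 1995-2015: "Sciensano holds a collection of >5,000 NIPD strains (1995-2015)". Section 1.4 also gives 1995 to 2015, and section 6.1 labels its retrospective time point 1995-2015 and requires 1,500 isolates for it. Section 11 budgets 1,500 retrospective isolates at €9.60 each, €14,400 in all.

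Other places stop a year earlier. Section 2 speaks of "more than 5,000 NIPD strains collected between 1995 and 2014 in Belgium". Section 1.5 describes a "nation-wide multicentre survey spanning nearly two decades (1995-2014)". Milestone M5 and the trend analysis in section 6.2 also use 1995-2014. On the collection itself, section 1.4 says: "For 12 consecutive winter periods, his team collected between 300 and 500 clinical isolates".

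On purpose, the summary names the comparison as serotype distribution by vaccination programme, and section 1.4 says the collection would serve to "retrospectively assess the impact of successive vaccination campaigns on serotype distribution among NIPD isolates in Belgium". Section 1.2 dates the programmes: "The national infant vaccination program was initiated in 2007 with PCV7", a change to PCV13 in 2011, a change to PCV10 in 2015-2016, and advice in December 2018 to go back to PCV13.

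For serotypes over time, section 6.1 sizes one contrast, all retrospective isolates against 2020-2022, and section 6.2 names a chi-square trend analysis. The prevalence ratios in 6.2 are stratified by age, gender and infection type; no programme period is named.

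**The concern.** There are two separate matters.

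First, the rule, the span and the total cannot all stand. A laboratory that follows 4.2 as written would type 150 isolates more than the budget pays for. One that works to 1,500 must drop a year that 4.2 and 6.1 include.

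Second, the analysis does not match the stated comparison. The infant programme widened and then narrowed its serotype cover, and widening it again has been advised. Vaccine-type shares may therefore fall and later rise. A trend test looks for a steady movement in one direction, and a pooled baseline averages the periods that the study wants to tell apart. The study could hold data that show a fall under PCV13 and a return afterwards, and still report no trend.

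**Working it through.** **Count.** Uneven years × 150:

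| Span | Where | Uneven years | Isolates | Cost at €9.60 |
|---|---|---|---|---|
| 1995-2014 | section 2, M5, 6.2 (also 1.5) | 10 (1995 to 2013) | 1,500 | €14,400 |
| 1995-2015 | 4.2, 6.1 (also 1.4) | 11 (1995 to 2015) | 1,650 | €15,840 |

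The stated 1,500 is reproduced on the first span only. The difference is 150 isolates, 10%, or €1,440.

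**Split of the 1,500 by programme.** 1995-2005 is six years, 900 isolates. If 2007 and 2011 count under the new programme, PCV7 has 2007 and 2009 (300) and PCV13 has 2011 and 2013 (300). If the two change years are left out, each of those periods has 150.

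**Assumptions for power.** The share is 50% before 2011, the sum of the PCV13 groups in 6.1 (7.5 + 7.5 + 5 + 30). It is 40% in the PCV13 years, a 20% relative fall; 6.1 does not say whether its 20% is relative or absolute. Tests are at the two-sided 5% level, isolates are independent, and the prospective sample is 1,500 or 2,250 (both in 6.1), placed at 2021.

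**Trend test, full return to 50%, prospective n = 1,500.**
- Mean year, weighted by isolates: (1,500 × 2004 + 1,500 × 2021) / 3,000 = 2012.5.
- The share departs from 50% only in 2011 and 2013, so the expected trend score is −0.10 × 150 × [(2011 − 2012.5) + (2013 − 2012.5)] = +15.
- Overall share 0.49. Sum of squares of year: 150 × 330 + 1,500 × 8.5² + 1,500 × 8.5² = 266,250. SD of the score: √(0.49 × 0.51 × 266,250) = 257.9.
- Standardised shift: 15 / 257.9 = 0.06, so power is about 5%. With 2,250 the mean year is 2014.2 and the shift is 66 / 278.2 = 0.24, so about 6%.

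The PCV13 years lie almost at the mean year, so a dip there hardly moves the slope.

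**Four-period chi-square (3 df), same scenario, 900 + 300 + 300 + 1,500.** Noncentrality = [2,700 × 0.01² + 300 × 0.09²] / (0.49 × 0.51) = 2.70 / 0.2499 = 10.8. Against the critical value 7.81, power is 80%.

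**All scenarios** (40,000 simulated studies; ranges are for 1,500 to 2,250 prospective isolates):

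| Share in 2020-2022 | Trend | Four periods, 2007 and 2011 assigned | Four periods, 2007 and 2011 left out |
|---|---|---|---|
| 50% (full return) | 5-6% | 80-81% | about 50% |
| 45% (partial return) | 68-71% | 85-87% | 71-75% |

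If the fall to 40% lasts into 2020-2022, the trend test has 99.9% power or more and nothing is lost.

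**Precision in the smaller periods.** 1.96 × √(0.25 / 300) = ±5.7 points for a 50% share.

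**The case against.** The best defence on the count is that 1995-2014 stands in four places and gives exactly the 1,500 that 6.1 and the budget use, so it is very probably what was meant and 2015 is a slip. I accept that as the likely intent. Sections 4.2 and 6.1 still carry the other span, and 4.2 is the instruction that will be followed.

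On the analysis, the trend test suits the lasting decrease that 6.1 plans for, the pooled contrast in 6.1 is well powered, and a statistical analysis plan not seen here may add a comparison by period. The first two stand. The low trend power needs an assumed full return. But a comparison by programme is the protocol's own stated comparison, and the protocol names a test that does not address it directly.

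Three stronger readings are tempting, and the documents do not support them.
- **That the draw can reach at most 1,050.** Twelve annual winters would touch at most 7 uneven years. But reference 30 is the tenth survey, from winter 2007-2008. Annual surveys would then run from 1998-1999 to 2009-2010, against a 1995 start and a 2012-2013 collection (1.4). The winters were evidently not annual. Each winter spanning two years contains one uneven year, so twelve of them could cover all ten.
- **That placing 60% of isolates (900 of 1,500) before 2007 is an error.** Section 1.4 values the collection because it predates the programmes. Moving to about 500 per period would lower trend power under partial return from 68-71% to 56%, and may not be feasible at 300 to 500 isolates per winter.
- **That the unstated meaning of 20% in 6.1 belongs to this point.** It is a separate matter of detail in 6.1.

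**Conclusion.** The point holds in two parts. The contradiction in span and total needs no assumption: 1,650 by 4.2 and the span in 6.1, against 1,500 stated and budgeted. It is small, 150 isolates or €1,440, and does not threaten the pooled comparison.

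The second part matters more. The serotype analysis in 6.2 relies on a trend test that is nearly blind to a fall under PCV13 followed by a full return (5-6% power), where a comparison by programme on the same isolates has about 80%. The size rests on the assumed shares, on 2007 and 2011 being assigned rather than left out, and on independent isolates. With a partial return the gain is smaller, and with a lasting fall there is none. It should be fixed before the retrospective typing planned for summer 2021. It does not invalidate the design.

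**What to change.** - **Sections 4.2 and 6.1:** use one span throughout. With 1995-2014, 10 × 150 = 1,500 and the budget stand. With 1995-2015, restate the total as 1,650 and the budget line as €15,840.
- **Section 4.2:** state which uneven years hold isolates, since 1.4 reports only 12 winters over the period, and how a winter spanning two calendar years is dated.
- **Section 6.2:** keep the trend test and add one comparison by programme period: before 2007, PCV7, PCV13, and 2020-2022. Fix before typing how 2007 and 2011 are assigned. Report the precision for the smaller periods, about 300 isolates each and ±5.7 points at a 50% share.

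Shifting part of the draw towards 2007-2014 is optional and has the costs given above.

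The cost is rewording, a short list of the years held and one extra test to report. No isolates are added if 1995-2014 is kept. Precision in the PCV7 and PCV13 periods stays modest.

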4.1 Prospective track

Regarding the prospective track (**Figure 6**), each month from September 2020 to May 2022 (20 months), twelve laboratories listed in **Table 1** committed to send the first 15 unduplicated isolates of *S. pneumoniae* collected from patients meeting the following criteria:

Inclusion criteria:

- Patients living in Belgium at the time of the study,
- from whom unduplicated *S. pneumoniae* isolates were collected in routine practices,
- from non-invasive upper (e.g.: pus/fluid from nasal sinus or from otitis media fluid) or lower respiratory tract (e.g. sputum bronchial or endotracheal aspirate, bronchoalveolar fluid (BAL),...) clinical samples.
- from patients diagnosed with pneumonia, sinusitis and otitis.

Exclusion criteria:

- Patients for whom *S. pneumoniae* was simultaneously isolated from blood or another usually sterile specimen.

Consequently, a theoretical maximal amount of 3,600 non-invasive *S. pneumoniae* isolates will be prospectively collected, although the actual number will probably be lower given the lower prevalence of NIPD during the summer period. For every shipped strain (with associated metadata) during the study period, the laboratory will be compensated by payment of €20.

The transfer of the isolates (under dry ice) from hospital laboratories to the “Sciensano Unit ‘Antibiotics & Resistance’ (Site Engeland - [name])” will be organised in the last week of every month, using the Sciensano internal sample transport service. Isolates will be accompanied by an electronic record sheet, listing the following metadata **upon availability** :

- isolate number
- Hospitalised (HOS), residing in a long-term care facility (LCF), ambulatory (AMB), or other (to be specified).
- admission date (hospitalised patients only)
- date of specimen collection
- patient age
- patient sex
- sample source including collection method
- clinical diagnosis
- vaccination status of the patient for *Streptococcus pneumoniae*
- For bacterial cultures from sputum, the amount of epithelial cells and white blood samples
- Other potential respiratory pathogens isolated (e.g. *H. influenzae*, *M. pneumoniae*, ...)

For all isolates sent, following analyses will be performed at Sciensano:

- Identification and confirmation of isolates by reference methods prior to use.
- Capsular typing using an FT-IR based method that will be developed in the scope of the project (section 5.4).

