5.4 Typing of cps genes

Capsular typing is performed according to the traditional Quellung reaction. However, in this project we will investigate the use of Fourier transform infrared (FT-IR) spectroscopy to predict the serotype of the most prevalent serotypes [32,33]. It has been reported that discriminatory biochemical fingerprints, observed on FT-IR spectra, consistently correlate with sugar-based coating structures that reflect strain variation. This will allow to perform capsular typing on a medium-throughput scale (96-well plate format), at less than €5 consumable cost per sample. The test will be validated, and published, in collaboration with the NRC for pneumococcal diseases. A downside of this test is that it relies on relative (comparative) measurements, with a large number of controls (n=24) being needed in every run. This implies collaboration with the NRC to traditionally type all strains that were nontypable using FT-IR.

To type nonencapsulated strains, the *cps* locus of the strain will be sequenced to classify the strain in group I (mutation or deletion in *cps* genes) or group II (replacement of the *cps* genes) NeSP. For this last group, 2 subgroups can be distinguished in function of genes that replace the *cps* locus. In the NCC1 subgroup (null capsule clade 1), the *pspK* gene is present, while in the NCC2 subgroup the *cps* genes are replaced by *aliC* and *aliD*.

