6.2 Evaluation

Our final goal is to investigate Belgian trends in serotype distribution in the non-invasive pneumococcal population. The statistical data analysis will be performed with Stat10 software (Stata Statistical Software: Release 13. College Station, TX), in collaboration with Sciensano's Epidemiology Service.

Using data from the Prospective/Retrospective surveillance track:

- Chi-square trend analysis of circulating serotypes within the non-invasive *S. pneumoniae* population, integrating retrospective data (1995-2014) with prospectively collected data (2020-2022). Data will be compared with the serotype dynamics of IPD, annually published by the NRC for pneumococcal diseases.

- Measurement of association strength within each stratum of age, gender and infection type by the prevalence ratios with exact Fisher tests for statistical significance. Particular attention will be given to NeSP isolates, their association with patient type and their influence on drug resistance.
- Chi-square trend analysis of antimicrobial resistance for all tested drug classes, in relation to historic data (1995-2013) and in association with serotype.
- Integrating metadata with WGS, we will perform phylogenetic analysis of sequenced isolates in their national and international context [13,14], and identification of genetic determinants of antibiotic resistance.

7 Access to source data and data in general

Neither of the funding partners can have a role in data collection and interpretation. However, funding partners can request at any time intermediate results or reports. The final report will be put under a six months embargo before open access publishing in Summer 2023.

8 Monitoring and quality assurance

All laboratory analyses will be performed according to ISO15089 standards. An internal project board consisting [name] (MD, PhD), [name] (Ir, PhD), [name] (Ir., PhD) and [name] (MD, PhD) will monthly follow up experimental results.

9 Adverse events

Not applicable.

10 Ethics

Upon approval of the project by at least two contact partners, a general and specific ethical application will be filed, in collaboration with Sciensano's legal department and GDPR officer. Approval of local and ethical committees will be sought.

11 Budget

PERSONNEL				
	Description	% Effort dedicated to this study	Institutional salary (3 years)	TOTAL
	Coordinating Scientist	0.6 FTE	€ 276,372	€ 165,823.2
	Statistician	0.2 FTE	-*	€ 0

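### All historical isolates are FT-IR typed in one season, so typing time largely coincides with the period compared, and no linking isolates are planned to check for drift

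*Protocol*

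**What the plan says.** Section 4.2 draws the historical set by year ("From every uneven year, we will randomly select 150 isolates") and types all of it with FT-IR in a single season: "Typing of the isolates of the retrospective study will be performed in the summer period of 2021". The reason given is that this is a time "when few isolates of the ongoing prospective study (2020-2022) are expected".

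Section 4.1 uses the same method for the prospective isolates. They are collected from September 2020 to May 2022, up to "a theoretical maximal amount of 3,600" isolates, and their transfer "will be organised in the last week of every month". No typing date or run allocation is given for them. Section 4.3 lists completion of typing for the two sets as separate milestones (M5 and M6).

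Section 5.4 names a drawback of the method, that "it relies on relative (comparative) measurements, with a large number of controls (n=24) being needed in every run". It adds that strains FT-IR cannot type go to the National Reference Centre (NRC) for traditional typing. Milestone M2 requires validation for 24 serotypes.

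Section 6.2 plans a chi-square trend analysis "integrating retrospective data (1995-2014) with prospectively collected data (2020-2022"). Section 6.1 also sizes a test of the shift in PCV13 serotypes between the two periods.

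**The concern.** When a relative measurement is made on one group in one season and on the other group mostly at other times, a change in the measurement looks like a difference between the groups. Such a change could come from the operator, the culture medium or the version of the spectral library. Here the groups are the periods whose serotype distributions are compared. Low overlap with prospective typing is the stated reason for the summer slot. The protocol does not plan to mix periods within runs, to type any isolate in both settings, or to conceal the period from the person typing.

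What is at stake is the reading of the historical versus 2020-2022 contrast. Drift in calling could add to a real serotype shift, hide one or imitate one. The analysis alone could not tell these apart, because it would have no isolates typed in both settings.

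**Working it through.** **Counts stated in the plan**
- Prospective maximum (4.1): 12 laboratories × 15 isolates × 20 months = 3,600, as stated.
- Historical set (4.2): 150 × 10 odd years (1995-2013) = 1,500, matching sections 6.1 and 11.
- Expected PCV13-type share (6.1): 7.5 + 7.5 + 5 + 30 = 50%.
- Prospective sample size for the main objective (6.1): 2,250.

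How section 6.1 derives 1,500 per period is a separate matter. The figure is used here only as the planned number.

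**How far typing time and period overlap**
- A 96-well plate with 24 controls leaves 96 − 24 = 72 study wells, assuming one well per sample and per control.
- Historical runs: 1,500 / 72 = 20.8, so 21 plates. Prospective runs: 2,250 / 72 = 31.3, so 32 plates (50 plates for 3,600).
- If summer means June to August (an assumption), at most 12 × 15 × 3 = 540 of 3,600 prospective isolates (15%) arrive then, and section 4.2 expects few.

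So the historical block is about 21 runs, each with its own controls. Some sharing of runs is possible, but the alignment with period is strong.

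**How much drift would matter**

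Suppose the true share is 50% in both periods and typing adds a net difference d between them. For n = 1,500 versus 2,250 the two-sided 5% threshold is

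1.96 × √(0.25/1,500 + 0.25/2,250) = 1.96 × 0.01667 = 3.3 points.

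The probability of a false significant result is Φ((d − 1.96·s0)/s1) + Φ((−d − 1.96·s0)/s1), where s0 is the pooled and s1 the unpooled standard error. Example for d = 5 points: s0 = √(0.52 × 0.48 × (1/1,500 + 1/2,250)) = 0.01665, s1 = √(0.55 × 0.45/1,500 + 0.25/2,250) = 0.01662, and Φ((0.05 − 0.03264)/0.01662) = Φ(1.04) = 85.2%.

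| Assumed net drift d | 1,500 vs 1,500 | 1,500 vs 2,250 | 1,500 vs 3,600 |
|---|---|---|---|
| 0 | 5.0% | 5.0% | 5.0% |
| 1 point | 8.5% | 9.2% | 10.0% |
| 2 points | 19.5% | 22.4% | 25.6% |
| 3 points | 37.6% | 43.7% | 49.7% |
| 5 points | 78.3% | 85.2% | 90.3% |
| Threshold | 3.6 points | 3.3 points | 3.0 points |

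In terms of miscalls, if 2%, 5% or 10% of PCV13-type isolates were called non-PCV13 in one batch only, the false change would be 0.50 × that rate = 1.0, 2.5 or 5.0 points. Of these, only the 10% case exceeds 3.3 points (50% versus 45%: z = 3.0).

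**If miscalls were equal in both periods**

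At 2-10% equal miscalling, the false-positive rate stays at 5%. A true 50% to 40% change would be seen as 9.8 to 9.0 points, with power above 99% at 1,500 per period. Only miscalling that differs between periods causes the problem.

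**The case against.** The strongest reply is that the protocol already guards against drift. The sentence that calls the method relative also requires 24 controls in every run. The test is validated for 24 serotypes first, and the NRC types what FT-IR cannot. Random run-to-run error averages out over about 21 historical and 32 prospective plates. This stands in large part: only systematic drift that survives the controls matters, and the document gives no evidence of any. The safeguards still leave a gap. Controls show that reference strains are called correctly, not that field isolates of both periods are called alike. The NRC fallback does not catch a confident wrong call. Validation before typing starts does not test stability over later batches.

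A reader might infer more than the text supports:
- **That the two sets never share a run.** Section 4.2 expects few prospective isolates in summer 2021, not none, and run allocation is not given for either track.
- **That vaccine effects in general become unreadable.** The historical years span the PCV7 (2007) and PCV13 (2011) introductions and are all typed in the same season. That schedule helps contrasts within 1995-2013.
- **That the age of the frozen stock is part of this problem.** Stock up to 26 years old (1995 to 2021) stays old on any plate. Prospective isolates are also frozen and regrown (5.1, 5.2).
- **That the study's primary estimate is at risk.** Section 6.1 calls the between-period shift the first secondary objective, although sections 0 and 2 frame the main aim more broadly, as serotype dynamics in both tracks.

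It is also fair to say that plate layout often sits in a laboratory procedure that is not shown here. But section 4.2 itself fixes the season, so a linking rule belongs beside it.

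**Conclusion.** The point holds as a design weakness with a cheap remedy, not as an error that invalidates the comparison. FT-IR typing time is largely aligned with period, and within-run controls are the main protection. Drift that passed them would fall on the historical versus 2020-2022 contrast.

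The size is conditional. With 1,500 versus 2,250 isolates and a 50% share, an observed difference of 3.3 points reaches significance, so a net drift of about that size would by itself give roughly even odds of a false finding. Smaller drifts still raise the error rate above 5%. Whether any such drift exists is not in the document. The drift values, the single-well layout and the constant 50% share are assumptions. It would go too far to conclude that an observed shift between the periods must be an artefact.

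**What to change.** In section 4.2:
- Allocate historical isolates to plates at random, balanced over collection year. This costs nothing. It also prevents collection year from following plate order, on which the protocol is silent.
- Keep 6-8 of the 72 study wells on each plate for coded, randomly chosen prospective isolates from September 2020 to May 2021. Up to 12 × 15 × 9 = 1,620 could be at Sciensano by then. Each is also typed in its own prospective run.
- Include a few coded historical isolates in later prospective runs.
- Send isolates with discordant calls to the NRC for traditional typing and report the agreement. If it is poor, qualify the between-period comparison.

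Use the repeats as a check only. Of about 150 linking isolates, some 75 would be PCV13 types. A 2%, 5% or 10% difference in miscalls gives about 1.5, 3.75 or 7.5 discordant calls. An exact McNemar test needs at least six, all in one direction, for p < 0.05 (2 × 0.5⁶ = 0.031). That is too few to estimate a numerical correction.

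Cost, taking EUR 5 per well (section 5.4 says less):
- 6 wells reserved: 1,500 / 66 = 22.7, so 23 plates. That is 23 × 6 = 138 repeats and 2 × 24 = 48 extra control wells: 186 × 5 = EUR 930.
- 8 wells reserved: 1,500 / 64 = 23.4, so 24 plates. That is 24 × 8 = 192 repeats and 3 × 24 = 72 extra control wells: 264 × 5 = EUR 1,320.

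The historical isolates repeated in later runs and some technician time come on top. The total budget in section 11 is about EUR 605,000. The change does not address differences due to the age of the stored stock.
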